## 5. DOSING DELAYS/DOSE MODIFICATIONS

Dose Level	Pioglitazone Dose
-1	15 mg, daily (1 tablet, 15 mg)
0	30 mg, daily (1 tablet, 30 mg)
+1	45 mg, daily (1 tablet, 45 mg)

Initial therapy is 30 mg po once daily. After 4 weeks, the dose is increased to 45 mg PO once daily and is maintained at that dose unless a dosage reduction is indicated, as described below. Excursions to this plan may be permitted based on medical need after consultation with the PI.

Weight gain of more than 5 pounds in the first week, or more than 15 pounds during therapy, prompts evaluation for fluid retention. If there is significant edema, the dose is reduced one level (45 mg to 30 mg; 30 mg to 15 mg; 15 mg to discontinue drug).

Serum ALT is measured every two months. Dosage reduction by one level is indicated if ALT exceeds 2.5x ULN.

Congestive heart failure of New York Heart Association Class II (slight limitation of physical activity; comfortable at rest, but ordinary physical activity results in fatigue, palpitation, or dyspnea), dosage reduction by one level. NYHA Class III (marked limitation of physical activity. Comfortable at rest, but less than ordinary activity causes fatigue, palpitation, or dyspnea), dosage reduction by two levels. NYHA Class IV (unable to carry out any physical activity without discomfort. Symptoms of cardiac insufficiency

at rest. If any physical activity is undertaken, discomfort is increased) discontinue pioglitazone.

The principal investigator may consider rechallenging with the prior dose should the toxicity resolve.

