### **3. PATIENT SELECTION**

#### **3.1 Inclusion Criteria**

3.1.1 Patients must have histologically confirmed thyroid carcinoma with the PAX8-PPARgamma translocation.

Refractory to radioactive iodine (RAI) as defined by: the tumor does not concentrate RAI; or the patient has had RAI within the last 16 months and has had progression despite that RAI; or the last RAI treatment was >16 months ago and the patient progressed after at least two RAI treatments; or the patient has received RAI treatments with a cumulative RAI dose of  $\geq 22.2$  GBq (600 mCi)

Not a candidate for surgery or RAI therapy with curative intent.

Lesions that would be treated by external beam radiation therapy (EBRT) based on standard of care can be so treated, but then cannot be used as target lesions unless there has been progression of the lesion since treatment (see criteria 3.1.7).

3.1.2 Measurable disease by RECIST 1.1 criteria.

3.1.3 Disease progression in the past 14 months.

3.1.4 Availability of histological material (primary tumor or metastases) for review of the diagnosis and demonstration of PAX8-PPARgamma fusion gene.

- 3.1.5 Adequate TSH suppression (<0.5 mIU/L)
- 3.1.6 Prior chemotherapy or surgery must have been completed at least 28 days prior to registration, and all toxicities must have resolved.
- 3.1.7 Prior radioactive iodine must have been completed at least 6 months prior to registration, or there must be documented disease progression since such therapy if it was within 6 months. Sites that have received EBRT must have disease progression post-EBRT to be used as sites of measurable disease.
- 3.1.8 Age  $\geq$ 18 years.
- 3.1.9 Life expectancy of greater than 6 months.
- 3.1.10 ECOG performance status 2 or less.
- 3.1.11 Patients must have normal organ function as defined below:
  - AST(SGOT)/ALT(SGPT)  $\leq$ 2.5 X institutional upper limit of normal (within 1 month of study Day 1)
- 3.1.12 Patients must be able to consume oral medications.
- 3.1.13 Women of childbearing potential must have a negative pregnancy test at baseline prior to receiving any study drug and must practice effective contraception while on study. (Pregnant or lactating patients are excluded).
- 3.1.14 All patients must sign an informed consent prior to enrollment.

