#### **4.3 Duration of Therapy**

Subjects will continue treatment for 28 weeks unless one of the following applies;

- Progressive Disease per RECIST criteria at any time
- Stable Disease per RECIST at 24 weeks
- Best Response per RECIST at 12 weeks and confirmed at 24 weeks
- Intercurrent illness that prevents further administration of treatment
- Unacceptable adverse events
- Patient decides to withdraw from the study
- General or specific changes in the patient's condition render the patient unacceptable for further treatment in the judgment of the investigator.

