#### 4.7 Study Calendar

	Pre-Study	Day 1	Wk 2	Wk 4	Wk 6	Wk 8	Wk 10	Wk 12	Wk 14	Wk 16	Wk 18	Wk 20	Wk 24/ EOT	Wk 28	Post treatment
Pioglitazone a		X													
Informed consent	X														
Demographics	X														
Medical history	X														
Concurrent meds	X														
Physical exam	X							X					X		
Vital signs	X							X					X		
Height	X														
Weight b															
Performance status	X							X					X		
Serum chemistry cd	X	X g				X				X			X		
CBC d	X	X g				X				X			X		
Thyroid blood tests de	X	X g					X						X		
β-hCG df	X														
Adverse event evaluation h	X		X	X				X			X		X		X
Tumor related imaging i	X							X					X	X	
Other correlative studies j	X												X		

a: Dose per protocol; orally administered once daily for 24-28 weeks..

b: Weight obtained at each study site visit and once/week on each subject's same home scale.

c: Pre-Study and Day 1 chemistries: bicarbonate, BUN, chloride, creatinine, glucose, potassium, SGOT[AST], sodium. At weeks 8, 16, 24: glucose, AST.

d: Blood tests can be performed locally.

e: TSH, Free T4, thyroglobulin, thyroglobulin antibodies. All thyroglobulin measurements are to be performed in the same laboratory. Serum thyroglobulin will not be used as a response parameter if endogenous antibodies invalidate the measurement.

f: Pregnancy test in women of childbearing potential only.

g: Within 1 month prior to administration of protocol therapy. Pre-Study assessments if within 1 month will suffice.

h: Adverse events evaluations at weeks 2, 4, 18 and post treatment (within 4 weeks and at 6 months) will be by telephone.

i: Baseline CT or MRI scans must be done within 4 weeks prior to the start of therapy. Baseline CT includes neck, chest and abdomen. Follow-up imaging for disease response is at sites of disease detected at baseline and must include abdomen in cases of elevated AST to evaluate for liver metastases. Week 28 confirmatory CT for patients who need such for RECIST criteria confirmation. Baseline MRI includes: areas with lesions on CT for which there is reasonable diagnostic uncertainty that may be clarified by MRI; and/or brain if clinically indicated.

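### The only liver-enzyme dose rule depends on ALT, but the study calendar's itemised chemistry list schedules AST and never ALT

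*Combined protocol and SAP*

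**What the plan says.** Section 5 (Dosing Delays/Dose Modifications) sets both a test and an action: "Serum ALT is measured every two months. Dosage reduction by one level is indicated if ALT exceeds 2.5x ULN". The other triggers in that section are weight gain with edema and heart failure by NYHA class. None of them uses a liver enzyme.

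The Study Calendar (Section 4.7) marks serum chemistry at Pre-Study, Day 1 and weeks 8, 16 and 24. Footnote c itemises the panel. For the first two time points: "Pre-Study and Day 1 chemistries: bicarbonate, BUN, chloride, creatinine, glucose, potassium, SGOT[AST], sodium". For the rest: "At weeks 8, 16, 24: glucose, AST". No other calendar row or footnote schedules ALT. Footnote d adds "Blood tests can be performed locally".

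AST has one stated use after baseline, in footnote i, where follow-up imaging "must include abdomen in cases of elevated AST to evaluate for liver metastases". That is an imaging instruction and not a dose rule.

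Outside Section 5, ALT appears only in eligibility criterion 3.1.11. That criterion writes AST and ALT with a slash between them, caps them at 2.5 times the institutional upper limit, and asks for the result within a month of Day 1. It does not say whether both enzymes are needed or either one will do.

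**The concern.** A dose rule can be applied only if the measurement it depends on is made. Here the rule reads ALT, while the one itemised list of chemistry tests provides AST. Section 6.1 counts liver toxicity and liver failure among the drug's known adverse events, so the gap falls on a recognised risk.

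There are two practical consequences. First, whether a patient has an ALT value may depend on which page was used to write the order. Since testing may be local, nothing in the calendar would bring the orders into line. Second, toxicity is a secondary objective, and Section 9.2 reports it as frequencies and percentages by grade and type. An ALT abnormality can be counted only where ALT was measured, so with about 15 patients a low count could mean few abnormalities or few tests.

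The mismatch may also reach baseline. If criterion 3.1.11 requires both enzymes, the Pre-Study list does not supply one of them. If either is enough, the scheduled AST meets it.

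**Working it through.** The plan gives no figure to reproduce here. The check sets the passages side by side and counts.

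**Inputs**
- Dose rule: ALT, every two months, with a one-level reduction above 2.5 times the upper limit (Section 5).
- Chemistry time points: Pre-Study, Day 1, weeks 8, 16 and 24 (Section 4.7, calendar row and footnote c).
- Patients: 15, or 14 after the one drop-out allowed for (Section 9.3).

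**Step 1. Does the timing agree?** Weeks 8, 16 and 24 are 8 weeks apart: 8 × 7 = 56 days. Two months is about 365.25 / 6 = 61 days. The two passages therefore appear to describe the same draws, and the disagreement is confined to the analyte.

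**Step 2. Which enzyme is listed, and where?**

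| Time point | AST listed | ALT listed |
|---|---|---|
| Pre-Study | yes | no |
| Day 1 | yes | no |
| Week 8 | yes | no |
| Week 16 | yes | no |
| Week 24 | yes | no |
| **Total** | **5 of 5** | **0 of 5** |
| **On treatment (weeks 8, 16, 24)** | **3 of 3** | **0 of 3** |

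Footnote g lets a Pre-Study draw taken within one month stand in for Day 1. In that case there are 4 separate draws, and the count is 4 of 4 against 0 of 4.

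**Step 3. How many results are at issue?** Results = on-treatment draws × patients completing 24 weeks.
- Calendar followed: AST 3 × 15 = 45; scheduled ALT 0 × 15 = 0.
- Section 5 applied at the same three draws: ALT 3 × 15 = 45.
- With 14 completers: 3 × 14 = 42.

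The possible ALT count therefore runs from 0 to 45.

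**Step 4. How many of those could change a later dose?** Under Section 4.3, patients with stable disease at week 24, or with a week-12 best response confirmed at week 24, stop then. A week-24 result can alter dosing only for those continuing toward week 28. Weeks 8 and 16 alone give 2 × 15 = 30 results. Patients who stop early for progression lower both figures.

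**Step 5. Is one term standing in for the other?** Footnote c spells the enzyme out as SGOT with AST in brackets and then repeats AST. Footnote i gives AST a purpose of its own. Section 5 names ALT twice. The documents do not show which passage, if either, contains a slip.

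**The case against.** The strongest reply is that Section 5 is itself an instruction to measure ALT. A protocol binds as a whole, so omitting ALT would be a deviation from Section 5, and the fault would be an incomplete footnote and not a rule without data. The study's monitoring committee also reviews adherence at least quarterly (Sections 6.3.1 and 6.3.2) and could notice missing results. This stands in part: ALT is not absent from the protocol, and someone working from Section 5 would draw it. It does not remove the contradiction, because the calendar is where the tests are itemised and it cuts the on-treatment list to two named analytes.

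A second reply is that this is a one-word slip, since the intervals match and criterion 3.1.11 pairs the two enzymes at the same multiple. That is possible. But AST has a separate use in footnote i, so replacing it with ALT would leave the imaging instruction without its test. The documents do not resolve the question, and a reader ordering tests cannot be expected to.

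Third, the range of 0 to 45 is simply none to all. It assumes every patient completes 24 weeks and says nothing about how many ALT elevations would be missed. This is correct: the documents give no ALT event rate, so the size can be stated only in tests. Nor does permission to test locally show that orders will differ; it only leaves room for it.

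Finally, other protections exist: the AST draws, withdrawal for "Unacceptable adverse events" (Section 4.3), departures from the dosing plan after consulting the principal investigator (Section 5), and quarterly review by the independent board (Section 6.3.4). They limit the harm, but none of them produces the ALT value that the rule calls for.

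**Conclusion.** The concern holds, and the inconsistency should be fixed. Section 5 makes ALT the trigger for the protocol's only liver-enzyme dose rule, and the calendar schedules ALT at none of its chemistry time points while scheduling AST at every one.

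The size is 0 of 3 scheduled on-treatment ALT draws, or 0 to 45 ALT results depending on which section is followed. The upper figure assumes that 15 patients complete 24 weeks and that Section 5's interval is applied at the calendar's three draws. About 30 of those results (weeks 8 and 16) would bear on later dosing in most cases. The number of ALT elevations that might go undetected cannot be estimated from the documents.

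The mismatch itself is certain from the text. That orders would actually diverge in practice is plausible but not shown. The point on criterion 3.1.11 is an ambiguity and becomes a second mismatch only if both enzymes are required. The primary endpoint, sample size and power are not affected.

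**What to change.** Reconcile Section 5, calendar footnote c and criterion 3.1.11:
- Make the dose rule and the calendar name the same enzyme or enzymes, scheduled at baseline and at each visit where the rule is applied.
- Say in criterion 3.1.11 whether both enzymes must meet the limit or either one suffices, and make the Pre-Study list match.
- If the AST entry changes, check that footnote i still has the test it relies on.

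Which enzyme and threshold should govern is a clinical decision for the investigators, and this review takes no position on it.

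The cost is a wording amendment and at most one extra analyte on samples already collected. It adds no visit and leaves the primary endpoint, sample size and power as they are.

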## **2. BACKGROUND**

### **2.1 Study Disease**

Follicular carcinoma and follicular variant of papillary carcinoma (together called follicular-patterned thyroid carcinomas) constitute about 15% of thyroid carcinomas. Approximately one-third of follicular carcinomas (1, 2), as well as a subset of follicular variant of papillary carcinomas that has been reported to vary from 0 – 38% (3, 4), contain a chromosomal translocation that fuses the genes encoding PAX8 and PPARgamma, resulting in the production of a PAX8-PPARgamma fusion protein (PPFP).

In general the therapy of thyroid cancer is surgical thyroidectomy followed by radioactive iodine (5). These therapies are effective in the majority of cases, resulting in a 10 year survival of ~85% in follicular carcinoma (6). However, distant metastases occur, primarily in the lung and less commonly in organs such as liver and bone. Metastatic disease is not always responsive to radioiodine – in some cases the tumor concentrates radioiodine but not at sufficient levels to cause a response, and in other cases the metastases do not concentrate radioiodine. There is no accepted chemotherapy or other therapy for these patients, and for these reasons, the median survival of AJCC stage IV follicular carcinoma is only ~4 years (6).

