## **3.2 Exclusion Criteria**

- 3.2.1 Patients may not be receiving any other investigational agents.
- 3.2.2 Patients with known untreated brain metastases.
- 3.2.3 History of allergic reactions attributed to compounds of similar chemical or biologic composition to pioglitzaone.
- 3.2.4 Diagnosis of diabetes mellitus or current therapy with any drugs used to treat diabetes mellitus, including but not limited to insulin, sulfonylureas, metformin, rosiglitazone (Avandia), and pioglitazone (Actos) within 14 days of study Day 1
- 3.2.5 Therapy with rosiglitazone (Avandia) or pioglitazone (Actos) at any time since the diagnosis of thyroid cancer.

- 3.2.6 Uncontrolled intercurrent illness including, but not limited to, ongoing or active infection, congestive heart failure, unstable angina pectoris, or cardiac arrhythmias.
- 3.2.7 Pregnant women are excluded from this study because pioglitazone is a U.S. Food and Drug Administration Pregnancy Category C drug. Because there is an unknown but potential risk for adverse events in nursing infants secondary to treatment of the mother with pioglitazone, breastfeeding should be discontinued if the mother is treated with pioglitazone.
- 3.2.8 No concurrent radiotherapy or chemotherapy may be given to the patient during the administration of the study drug.
- 3.2.9 Patients with uncontrolled malabsorption syndromes.
- 3.2.10 Patients with a history of congestive heart failure of any New York Heart Association class.
- 3.2.11 Any medical or psychiatric illness which, in the opinion of the principal investigator, would compromise the patient's ability to tolerate this treatment regimen.
- 3.2.12 Use of rifampin (strong CYP2C8 inducer) within 14 days of study Day 1.
- 3.2.13 Other current malignancy than the disease under study.
- 3.2.14 Grade 2 or worse edema within 14 days prior to study Day 1, per CTCAE v4.

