## **4. TREATMENT PLAN**

### **4.1 Pioglitazone Administration**

This study will be conducted under an exemption of IND (# 113,492) granted by the FDA. Pioglitazone will be obtained from an outpatient pharmacy using a prescription issued by a study investigator.

Drug information is available in the drug package insert (See link in Appendix D).

Treatment will be administered on an outpatient basis. Reported adverse events and potential risks are described in Section 6. Appropriate dose modifications for

pioglitazone are described in Section 5. No investigational or commercial agents or therapies other than those described below may be administered with the intent to treat the patient's malignancy.

Pioglitazone will be administered once daily without regard to meals. The initial dosage will be 30 mg daily, increased to 45 mg after 4 weeks unless side effects require otherwise.

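### Section 5 allows rechallenge at the prior dose with no limit by NYHA class, so a patient cut to 15 mg for Class III heart failure may return to 45 mg in one step

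*Combined protocol and SAP*

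**What the plan says.** Section 5 sets three dose levels: 15, 30 and 45 mg daily. Section 4.1 gives the planned titration: "The initial dosage will be 30 mg daily, increased to 45 mg after 4 weeks unless side effects require otherwise".

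For heart failure, Section 5 reduces the dose one level for NYHA Class II. For Class III the rule reads "Comfortable at rest, but less than ordinary activity causes fatigue, palpitation, or dyspnea), dosage reduction by two levels". For Class IV it reads "at rest. If any physical activity is undertaken, discomfort is increased) discontinue pioglitazone".

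After these rules, and after those for edema and ALT, the section closes with "The principal investigator may consider rechallenging with the prior dose should the toxicity resolve". Near its start it also has a general allowance: "Excursions to this plan may be permitted based on medical need after consultation with the PI". Neither sentence mentions NYHA class.

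Three other places bear on the point. Criterion 3.2.10 excludes "Patients with a history of congestive heart failure of any New York Heart Association class". Section 4.3 lists "Unacceptable adverse events" among the reasons to end treatment, and Section 4.5 removes from study any patient who meets a Section 4.3 criterion. Section 6.1 cites the boxed warning and calls for strict monitoring for heart failure, with immediate reporting of weight gain, new edema and new dyspnea.

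**The concern.** The way down is graded by severity and the way up is not. A patient who has just recovered from Class III heart failure may be taken to the top dose faster than a patient who has never had heart failure. Heart failure is also the risk that the protocol singles out for special monitoring, so one would expect the rechallenge rule to be tightest there.

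What is at stake is the safety of a small number of patients. A rule that names the prior dose gives the principal investigator written cover for a one-step return after a serious cardiac event, and a site applying it would not be deviating from the protocol.

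**Working it through.** The plan states no figure on this point. The check applies the Section 5 dose levels to each heart failure rule, then applies the closing sentence as written.

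**Inputs.** Dose levels 15, 30 and 45 mg (Section 5). Start at 30 mg, with 45 mg after 4 weeks (Sections 4.1 and 5). Class II is one level down, Class III two levels down, and Class IV stops the drug (Section 5). The prior dose is taken to be the dose before the reduction, which is the ordinary meaning.

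| NYHA class | Dose at event | After the reduction rule | Return under the closing sentence |
|---|---|---|---|
| II | 45 mg | 30 mg | 45 mg: one level, 45/30 = 1.5-fold |
| II | 30 mg | 15 mg | 30 mg: one level, 30/15 = 2-fold |
| II | 15 mg | no level left | 15 mg |
| III | 45 mg | 15 mg (45 to 30 to 15) | 45 mg: two levels, 45/15 = 3-fold |
| III | 30 mg | no level left | 30 mg |
| III | 15 mg | no level left | 15 mg |
| IV | any | stopped | not stated |

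**The clear case** is Class III at 45 mg. The planned escalation for a new patient is 30 to 45 mg, one level and 1.5-fold, after 4 weeks at 30 mg. The permitted return is 15 to 45 mg, two levels and 3-fold, with no time at 30 mg. It is the only row in which a patient still on drug can rise by more than one level at once.

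**Where no dose is left.** For edema, Section 5 spells out that the step below 15 mg is to stop the drug. The heart failure rules do not, though the same reading is natural. The closing sentence, taken literally, would still point back to 30 or 15 mg.

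**Class IV.** The instruction is to stop. Section 4.3 ends treatment for unacceptable adverse events, Section 4.5 then removes the patient from study, and no provision for re-entry appears. Together these make the stop final on an ordinary reading. What is missing is the explicit link: unacceptable is not defined by NYHA class, and the closing sentence exempts nothing.

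**Effect on the analysis.** Under Sections 8.1.1 and 9.2, a patient who comes off therapy for unacceptable adverse events at any time is evaluable for response. A patient held at 15 mg is evaluable on the usual terms. The count of evaluable patients does not depend on which rechallenge rule is used.

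**The case against.** The strongest reply is that the sentence is permissive and conditional. The principal investigator may decline to rechallenge, may go through 30 mg first, and may act only once the toxicity has resolved. This stands. A reader might infer that the protocol directs a jump back to 45 mg; it does not.

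A reader might also infer that the protocol allows restart after Class IV. The documents do not support that either. Returning to a prior dose fits a reduced dose better than a stopped drug, and Sections 4.3 and 4.5 point to a final stop. What survives is only that the sentence leaves this unsaid.

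Nor does criterion 3.2.10 contradict Section 5. It governs entry, and because it excludes every class it cannot justify drawing a line between Class II and Class III. That line rests instead on Section 5's own grading, which treats Class III more severely than Class II.

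The event would be rare. About 15 patients are planned, and a history of heart failure, uncontrolled cardiac illness and recent grade 2 or worse edema are all excluded. The clear case needs Class III at 45 mg, then resolution, then a decision to return in one step. Monitoring is also real: weekly home weights, immediate symptom reporting, the investigator's power to stop, and quarterly independent board review. None of these limits rechallenge by class.

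Finally, Section 2.1 says "There is no accepted chemotherapy or other therapy for these patients", which argues for leaving some discretion. That is a fair cost to weigh. It is softened because the patient in the clear case stays on 15 mg.

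**Conclusion.** The point holds in limited form. Section 5 names the prior dose as the rechallenge dose for any resolved toxicity, no other section limits this by NYHA class, and the literal result after Class III at 45 mg is a permitted two-level, 3-fold return. For Class IV the gap is one of explicitness only.

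The conclusion rests on two assumptions: that the prior dose means the dose before the reduction, and that nothing outside these documents restricts rechallenge. The package insert is cited in Section 4.1 and Appendix D but is only linked, so its content could not be checked. The documents give no rate for Class III or IV heart failure, so no frequency is claimed. The case rests on the severity of the event and the low cost of the change. It is worth considering as a safety amendment and has no bearing on endpoint, power or analysis.

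**What to change.** Replace the closing sentence of Section 5 with text to this effect:

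- After NYHA Class III heart failure there is no re-escalation. A patient who was on 45 mg continues at 15 mg; a patient who was on 30 or 15 mg discontinues.
- Discontinuation for Class IV heart failure is permanent.
- The allowance for excursions earlier in the section does not override these two rules.
- For Class II heart failure, edema and ALT elevation, once the toxicity has resolved, the principal investigator may consider re-escalation one dose level at a time.

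The cost is a few lines of wording. The downside is that the principal investigator loses discretion in a rare case, in a disease for which the protocol sees no accepted alternative. If that loss is thought too great, requiring one-level steps after Class III as well would remove the jump past 30 mg, but it would still allow a return to the dose at which Class III heart failure occurred. Sample size, evaluability and analysis stay as they are.
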